**Table 5: Adverse Event Causality Assessment**

Term	Relationship	Definition
Related	Yes	The temporal relationship between the event and the administration of the investigational product is compelling and/or follows a known or suspected response pattern to that product, and the event cannot be explained by the subject’s medical condition, other therapies, or accident.
Not Related	No	The event can be readily explained by other factors such as the subject’s underlying medical condition, concomitant therapy, or accident and no plausible temporal or biologic relationship exists between the investigational product and the event.

### 8.1.3 Outcome Categorization

The outcome of AEs must be recorded during the course of the study on the CRF. Outcomes are as follows:

- Fatal
- Not Recovered/Not Resolved
- Recovered/Resolved
- Recovered/Resolved with Sequelae
- Recovering/Resolving
- Unknown

### 8.1.4 Symptoms of the Disease Under Study

Subjects with SNHL associated with speech-in-noise impairment may experience the onset of tinnitus, hyperacusis, and reduced hearing capability consistent with the spectrum hearing loss symptomatic progression.

Symptoms of the disease under study should not be classed as AEs as long as they are within the normal day-to-day fluctuation or expected progression of the disease. However, significant worsening of the symptoms should be recorded as an AE.

### 8.1.5 Clinical Laboratory Evaluations

A change in the value of a clinical laboratory investigation can represent an AE if the change is clinically relevant or if, during treatment with the IP, a shift of a parameter is observed from a normal value to an abnormal value, or a further worsening of an already abnormal value. When evaluating such changes, the extent of deviation from the reference range, the duration until return to the reference range, either while continuing treatment or after the end of treatment with the IP, and the range of variation of the respective parameter within its reference range, must be taken into consideration.

If, at the end of the treatment phase, there are abnormal clinical laboratory values which were not present at baseline, further clinical or laboratory investigations should be performed until the values return to within the reference range, the value stabilizes, or until a plausible explanation (e.g., concomitant disease) is found for the abnormal clinical laboratory values.

The Investigator should decide, based on the above criteria and the clinical condition of a subject, whether a change in a clinical laboratory parameter is clinically significant and therefore represents an AE.

### 8.1.6 Pregnancy

All pregnancies are to be reported from the time informed consent is signed until the final visit is completed at approximately 90 days post-injection. Any report of pregnancy for any female subject

or the partner of a male subject must be reported within 1 business day to the Sponsor ([Table 1](#)) using the Pregnancy Report Form. Since this is a single dose study, no further dosing will be administered to the subject and the subject will continue to be followed according to the SOE, unless, at the discretion of the Investigator, specific tests are contraindicated for the pregnancy.

If the female subject and/or female partner of a male subject agrees to the primary care physician being informed, the Investigator should notify the primary care physician that the subject/female partner of the subject was participating in a clinical study at the time she became pregnant and provide details of treatment the subject received.

Every effort should be made to gather information regarding the pregnancy outcome and condition of the infant. It is the responsibility of the Investigator to obtain this information within 30 calendar days after the initial notification and approximately 30 calendar days post-partum.

Pregnancy complications such as spontaneous abortion/miscarriage or congenital abnormality are considered SAEs and must be reported using the SAE Form. Note, an elective abortion is not considered an SAE.

### **8.1.7 Medication Error**

Medication error (as defined below) must be reported to the Sponsor according to the SAE reporting procedure whether or not they result in an AE/SAE as described previously in this section. Note: The 1 business day reporting requirement for SAEs does not apply to reports of medication errors unless these result in an SAE.

- **Medication Error** – An error made in prescribing, dispensing, administration, and/or use of an IP.

## **8.2 Serious Adverse Event Procedures**

### **8.2.1 Reference Safety Information**

The reference for safety information for this study is the IB which the Sponsor has provided under separate cover to all Investigators.

### **8.2.2 Reporting Procedures**

All initial and follow-up SAE reports must be reported by the Investigator to the Pharmacovigilance contact within 1 business day of the first awareness of the event. Note: The 1 business day reporting requirement for SAEs does not apply to reports of medication errors (see [Section 8.1.7](#)) unless they result in an SAE.

The Investigator must complete, sign, and date the SAE Form and verify the accuracy of the information recorded on the form with the corresponding source documents (Note: Source documents are not to be sent unless requested) and fax or e-mail the form to the Pharmacovigilance Department ([Table 1](#)).

### 8.2.3 Serious Adverse Event Definition

A *Serious Adverse Event* (SAE) is any untoward medical occurrence (whether considered to be related to IP or not) that at any dose:

- Results in death
- Is life-threatening

**NOTE:** The term 'life-threatening' in the definition of 'serious' refers to an event in which the subject was at risk of death at the time of the event; it does not refer to an event which hypothetically might have caused death if it was more severe.

- Requires inpatient hospitalization or prolongation of existing hospitalization
- Results in persistent or significant disability/incapacity
- Is a congenital abnormality/birth defect
- Is an important medical event; Note: Important medical events that may not result in death, be life-threatening, or require hospitalization may be considered an SAE when, based upon appropriate medical judgment, they may jeopardize the subject and may require medical or surgical intervention to prevent one of the outcomes listed in this definition. Examples of such medical events include allergic bronchospasm requiring intensive treatment in an emergency room or at home; blood dyscrasias or convulsions that do not result in inpatient hospitalization; or the development of drug dependency or drug abuse.

Hospitalizations, which are the result of elective or previously scheduled surgery for pre-existing conditions, which have not worsened after initiation of treatment, should not be classified as SAEs. For example, an admission for a previously scheduled ventral hernia repair would not be classified as an SAE.

However, complication(s) resulting from a hospitalization for an elective or previously scheduled surgery that meets serious criteria must be reported as SAE(s).

### 8.2.4 Serious Adverse Event Collection Timeframe

All SAEs are collected from the time the subject signs informed consent until the final study visit at approximately 90 days post-injection. All SAEs occurring during this period must be reported to the Pharmacovigilance contact ([Table 1](#)) within 1 business day of the first awareness of the event.

### 8.2.5 Serious Adverse Event Onset and Resolution Dates

The onset date of the SAE is defined as the date the event meets serious criteria. The resolution date is the date the event no longer meets serious criteria, the date the symptoms resolve, or the event is considered chronic. In the case of hospitalizations, the hospital admission and discharge dates are considered the onset and resolution dates, respectively.

In addition, any signs or symptoms experienced by the subject prior to study entry or leading up to the onset date of the SAE or following the resolution date of the SAE, must be recorded as an AE, if appropriate.

#### **8.2.6 Fatal Outcome**

Any SAE that results in the subject's death (i.e., the SAE was noted as the primary cause of death) must have fatal checked as an outcome with the date of death recorded as the resolution date. For all other events ongoing at time of death that did not contribute to the subject's death, the outcome should be considered not resolved, without a resolution date recorded.

For any SAE that results in the subject's death or any ongoing events at the time of death, the action taken with the IP should be recorded as "dose not changed" or "not applicable" (if the subject never received IP).

#### **8.2.7 Regulatory Agency, Institutional Review Board, Independent Ethics Committee, and Site Reporting**

The Sponsor is responsible for notifying the relevant regulatory authorities and the Contract Research Organization (CRO) is responsible for notifying study sites and the central IRB of related, unexpected SAEs.

In addition, Sponsor is responsible for notifying active sites of all related, unexpected SAEs occurring during all interventional studies across the PIPE-505 program.

The Investigator is responsible for notifying his/her local IRB or the relevant local regulatory authority of all SAEs that occur at his or her site as required.

## 9. DATA MANAGEMENT AND STATISTICAL METHODS

### 9.1 Data Collection

An eCRF for each subject will be provided. All appropriate subject data gathered during the study will be recorded in English on these forms. Whenever possible, all information requested on the eCRF should be completed. If information is not available, it should be documented as such.

### 9.2 Clinical Data Management

Quality control and data validation procedures are applied to ensure the validity and accuracy of the clinical database.

Data are to be reviewed and checked for omissions, errors, and values requiring further clarification using computerized and/or manual procedures. Data queries requiring clarification are to be communicated to the site for resolution. Only authorized personnel will make corrections to the clinical database, and all corrections are documented in an auditable manner.

The completed CRFs or completed print out and/or electronic copy of the eCRFs for this study are the property of Pipeline and should not be made available to third parties, except for authorized representatives of appropriate health/regulatory authorities, without written permission from Pipeline.

### 9.3 Statistical Analysis Process

Details regarding the statistical methods and definitions will be provided in the Statistical Analysis Plan (SAP). The SAP will serve as a complement to the protocol and supersedes it in case of differences. The SAP will be finalized prior to unblinding to preserve the integrity of the statistical analysis and study conclusions.

All statistical analyses will be performed after the database is locked and unblinded. Statistical analyses will be performed using Version 9.4 or higher of SAS® (SAS Institute, Cary, NC 27513). Summary tables and listings of data will be provided. Summary statistics will be presented by dose group and for all subjects combined as appropriate. For continuous variables, data will be summarized with the number of subjects (N), mean, standard deviation, median, minimum, and maximum by treatment group. For categorical variables, data will be tabulated with the number and proportion of subjects for each category by treatment group.

### 9.4 Selection of Subjects to be Included in the Analyses

**Enrolled Set** – Subjects who have signed informed consent and have begun some study procedures (e.g., dispensed IP current drug has been withdrawn).

**Randomized Set** – Enrolled subjects for whom a randomization number has been assigned.

**Safety Analysis Set** – Enrolled/Randomized subjects who have undergone dosing of IP. Safety data for these subjects will be summarized by treatment actually received.

**Full Analysis Set** – Subjects in the Safety Analysis Set who have at least 1 post-baseline value efficacy assessment. Efficacy data will be summarized by assigned treatment regardless of actual treatment taken.

**Per-Protocol Set** – Subjects in the Full Analysis Set who do not have pre-defined protocol deviations and who completed the final scheduled assessment.

**Pharmacokinetic Set** – Subjects in the Safety Analysis Set with no major deviations related to IP intake, for whom the primary PK data is considered sufficient and interpretable.

## 9.5 Subject Disposition

Disposition of subjects in each analysis set will be summarized by treatment group using descriptive statistics. In addition, for subjects who prematurely discontinue from the study, the reasons for discontinuation will be summarized by treatment group.

## 9.6 Demographic and Baseline Characteristics

Descriptive summaries of demographic and baseline characteristics will be presented by treatment group and overall for the Safety Analysis Set and Full Analysis Set (FAS).

Demographics and baseline characteristics will be examined to assess the comparability of the treatment groups at baseline. Continuous variables such as subject age, weight, height, and body mass index (BMI) will be summarized using number of observations, mean, standard deviation, median, minimum, and maximum values. Categorical variables such as subject sex and race will be summarized using number of observations and percentages for each category.

Medical history and history of SNHL will be summarized by treatment group using the number of observations and percentages of subjects reporting each category.

## 9.7 Prior and Concomitant Medication

Prior and concomitant medications will be coded using the most current version of the WHO drug dictionary, as of the start of the study. Prior and concomitant medications will be listed and summarized by therapeutic area preferred drug name and treatment group.

## 9.8 Safety Analyses

AEs will be coded using the most current version of Medical Dictionary for Regulatory Activities (MedDRA) as of the start of the study. The number of events, incidence, and percentage of treatment-emergent adverse events (TEAE) will be calculated overall, by system organ class (SOC), and by preferred term. Events with missing onset dates will be included as treatment-emergent. Treatment emergent events are considered those events with onset dates on or after

study drug exposure or events with dates of onset or worsening after study drug exposure. If a subject experiences more than one occurrence of the same AE, the occurrence with the greatest severity and the closest association with the study drug will be summarized. TEAEs will be further summarized by severity and relationship to IP. AEs related to IP, AEs leading to withdrawal, SAEs, and deaths will be summarized/listed.

Clinical laboratory tests, vital signs, and ECG findings will be summarized by treatment group and visit. Change from baseline values will be summarized using shift tables. Potentially clinically important findings will also be summarized or listed.

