## 2.2 Endpoints

### 2.2.1 Primary Endpoint

The primary endpoint of the study is the number and severity of AEs up to 3 months following a single unilateral intratympanic injection of PIPE-505.

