## 6.3 Administration of Investigational Product(s)

### 6.3.1 Index Ear Selection and Dosing Procedure

The IP or Placebo will be administered by an intratympanic injection as an out-patient procedure by a qualified otologist or neuro-otologist. The ear selected for dosing (i.e., the Index Ear) will be identified based on the audiometry and QuickSIN results at Screening as follows:

- The ear with the worse audiometry, as determined by the PI, will be identified as the Index Ear.
- If both ears are equal by audiometry, the ear with the highest SNR on the QuickSIN will be defined as the Index Ear.
- If the audiometry and QuickSIN are equal in each ear, the PI and subject will determine the Index Ear.

Otoscopy of the Index Ear canal and TM will be performed prior to administration and excessive earwax or debris will be manually cleared. At the discretion of the otologist or neuro-otologist performing the intra-tympanic injection, a topical anesthetic (e.g., EMLA cream [eutectic lidocaine/prilocaine mixture] or xylocaine [4% lidocaine solution or 10% pump spray]) may be applied to the external tympanic membrane. Given the transient discomfort associated with topical anesthesia and the extremely small gauge of the needle used for injection, the Investigator may also elect to perform the intra-tympanic injection without use of a topical anesthetic, after discussion with the subject. If applied, any remaining anesthetic in the external canal will be suctioned off prior to the injection in order to avoid spillage into the tympanic cavity and possible vertigo or dizziness. Any local anesthetic, if utilized, should be recorded in the subject's source record and the Concomitant Medications case report form.

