## 8. ADVERSE AND SERIOUS ADVERSE EVENTS ASSESSMENT

### 8.1 Definition of Adverse Events, Period of Observation, Recording of Adverse Events

An *Adverse Event* (AE) is any untoward medical occurrence in a clinical investigation subject administered a pharmaceutical product and that does not necessarily have a causal relationship with this treatment. An AE can therefore be any unfavorable and unintended sign (including an abnormal laboratory finding), symptom, or disease temporally associated with the use of a medicinal (investigational) product, whether or not related to the medicinal (investigational) product (ICH Guidance E2A,1995).

All AEs should be captured on the AE CRF.

All AEs are collected from the time the informed consent is signed until the final visit is completed at approximately 90 days post-injection. All AEs are to be recorded on the appropriate AE pages in the CRF and in source documents. Where possible, a diagnosis, rather than a list of symptoms, should be recorded. If a diagnosis has not been made, then each symptom should be listed individually. In addition to untoward AEs, unexpected benefits outside the IP indication should also be captured on the AE CRF.

All AEs must be followed to closure (the subject's health has returned to his/her baseline status or all variables have returned to normal), an outcome is reached, stabilization (the Investigator does not expect any further improvement or worsening of the event), or the event is otherwise explained regardless of whether the subject is still participating in the study. When appropriate, medical tests and examinations are performed so that resolution of event(s) can be documented.

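### Protocol 9.8 makes every adverse event with a missing onset date treatment-emergent, even when its stop date is before dosing (minor)

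*Protocol*

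**What the plan says.** The rule for missing dates is in Protocol 9.8: "Events with missing onset dates will be included as treatment-emergent". The general definition in that section opens: "Treatment emergent events are considered those events with onset dates on or after". The reference point of that clause is exposure to study drug. A second clause, joined to it as an alternative, covers a start or a worsening later than that point. The output is described in the same section: "The number of events, incidence, and percentage of treatment-emergent adverse events (TEAE) will be calculated overall", with further breakdowns by system organ class, preferred term, severity and relationship.

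What the trial is chiefly meant to measure is set out in Protocol 2.2.1, which reads: "The primary endpoint of the study is the number and severity of AEs up to 3 months following a single unilateral intratympanic injection of PIPE-505".

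Protocol 8.1 sets the collection window: "All AEs are collected from the time the informed consent is signed until the final visit is completed at approximately 90 days post-injection". Section 7.1.1 allows screening up to 56 days before randomization, and section 6.3.3 puts randomization and dosing on the same day, Day 0. Section 8.1.1 asks for start and stop dates for each change in severity. It also asks that a pre-treatment event that worsens after dosing be recorded as a new AE.

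Protocol 9.3 lets the SAP prevail where the two documents differ. The SAP table of contents lists section 10.2, Adverse Events, but the text of that section is not in the public copy.

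**The concern.** Counting an event of unknown onset as treatment-emergent is a normal, cautious convention. It is cautious only while the timing really is unknown. If the onset date is blank but the stop date is before Day 0, the timing is settled: the event was over before the needle went in. The 9.8 sentence ignores that information.

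Such records can exist, because the AE database opens at consent and can hold up to eight weeks of pre-dose events per subject. An event of this kind would enter the overall, organ-class, preferred-term and severity tables. Section 9.8 also reports the most severe of repeated occurrences of the same AE, so a pre-dose occurrence could set the severity shown for a subject whose post-dose occurrence was milder. This is a first-in-human trial whose main result is a descriptive AE count in 18 and 6 subjects, so single events are visible.

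**Working it through.** The documents state no figure that depends on this rule, so there is nothing to reproduce. The check has two parts.

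**1. Apply the rule to test events.** The inputs are the 9.8 wording, collection from consent (8.1), and recorded stop dates (8.1.1). The word exposure in 9.8 can mean the dosing date or the moment of injection, so both readings are shown.

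| Test event | As written, exposure = date | As written, exposure = moment | With the proposed wording |
|---|---|---|---|
| Onset missing, stop Day -10 | counted | counted | not counted |
| Onset missing, stop Day 5 | counted | counted | counted |
| Onset Day 0, 1 h before injection | counted | not counted | depends on the stated meaning of exposure; counted if the order is unknown |
| Onset Day 0, 1 h after injection | counted | counted | counted |
| Onset Day -3, no worsening | not counted | not counted | not counted |

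The first row is the defect. The event is demonstrably pre-dose and is counted under either reading. The last row shows the inconsistency: an equally pre-dose event is left out simply because its onset date was filled in. The third row is an ambiguity, not a plain inclusion.

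**2. Possible size.** The arms are 18 PIPE-505 and 6 placebo (Protocol 9.12).

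- Largest shift in an incidence from one subject: 1/18 = 5.6 points on PIPE-505, 1/6 = 16.7 points on placebo. These are maxima. If the subject already has a treatment-emergent event in that row of the table, the incidence does not move, although the event count rises by one.
- No rate is given, so let q be an assumed proportion of subjects with one such event, independent between subjects. The expected number is 18q on PIPE-505 and 6q on placebo. The chance of at least one among 24 is 1 - (1 - q)^24.

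| Assumed q | Expected, PIPE-505 | Expected, placebo | Chance of at least one in 24 |
|---|---|---|---|
| 1% | 0.18 | 0.06 | 21% |
| 2% | 0.36 | 0.12 | 38% |
| 5% | 0.90 | 0.30 | 71% |
| 10% | 1.80 | 0.60 | 92% |

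An event that ended before the injection cannot have been caused by the assigned treatment. Under randomization q is therefore the same in both arms, and the expected difference in incidence from this source alone is q - q = 0. What remains is inflation of both arms and chance imbalance.

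**The case against.** **The governing text may already deal with this.** The SAP prevails over the protocol, and its section 10.2 cannot be read in the public copy. This stands: the point can be made only against the protocol sentence, and the SAP must be checked before anything is changed.

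**The pattern should be rare.** Start dates are required (8.1.1) and omissions are queried (9.2), so a blank onset with a known pre-dose stop should be uncommon. This also stands. It is why the rates above are only assumptions, with the low end more plausible.

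**Relationship is tabulated separately.** Under Table 5 an event that ended before dosing should be classed as not related. That protects the relatedness table but not the overall, organ-class, preferred-term and severity counts.

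**A stronger reading of Day 0 is tempting.** A reader might infer that 9.8 also counts events known to have begun on Day 0 before the injection. Ear clearing and optional anesthetic come first, and section 6.3.1 speaks of discomfort: "Given the transient discomfort associated with topical anesthesia". The documents do not support that reading:

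- If exposure means the injection, an earlier onset is excluded.
- If only dates are held, such an event is indistinguishable from a post-dose one, so it is not known to be pre-dose.
- That the AE form has no onset time is inferred from silence, since the form is not part of the documents.
- Section 6.3.1 gives the discomfort as a reason why the anesthetic may be omitted. It does not call it an AE.

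What is left for Day 0 is a request to define a term.

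**Conclusion.** The point holds as a minor correction to the missing-onset rule. As the protocol is written, an AE with no onset date and a stop date before dosing is treatment-emergent, which conflicts with a primary endpoint restricted to AEs following the injection.

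The size cannot be derived from the documents. The bound is one subject's worth of incidence per misclassified subject, 16.7 points on placebo or 5.6 on PIPE-505. The direction is upward in both arms, with no expected bias between them.

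A reader might go further and infer that the primary AE count does contain pre-dose events. That is not shown. It would need at least one record with a blank onset and a pre-dose stop date, and SAP 10.2 would have to carry the same rule. Section 9.8 also does not expressly name the treatment-emergent count as the primary endpoint analysis, although it is the only AE count that the protocol describes.

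**What to change.** 1. Read SAP section 10.2. If it already uses stop dates and partial dates to classify such events, no change to the SAP is needed.
2. Amend the sentence in Protocol 9.8, and SAP 10.2 only if it repeats the protocol rule. Suggested sense: an AE with a missing or partial onset date is treatment-emergent unless its stop date, or the known part of its onset date, places it before the injection without later worsening; every undetermined case remains treatment-emergent. Section 8.1.1 already makes worsening after dosing a new record, so the exception loses no post-dose event.
3. As a clarification only, state whether study drug exposure means the dosing date or the moment of injection for Day 0 onsets, and keep Day 0 events of unknown order as treatment-emergent.

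The cost is one or two sentences and a small change to the derivation of the treatment-emergent flag, settled before unblinding. It needs no extra visits or assessments, and the cautious default for unknown timing is kept.
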